Institut für diagnostische und interventionelle Radiologie

[name]. med. [name]

Direktor der Klinik und Poliklinik für Nuklearmedizin

[name]. med. [name]

Direktor der Medizinischen Klinik und Poliklinik II

16. Appendix

Wissenschaftsberater, [name] [name], [name]

Schätzung der Fallzahl für das Forschungsvorhaben CXCR4 Expression bei Systemischer Sklerose – Interstitielle Lungenerkrankung (SSc-ILD) mittels a priori Teststärke-Analyse

In der vorliegenden Studie soll die CXCR4 Expression mittels Positronen-Emissions-Tomografie (PET) bei SSc-ILD untersucht werden.

Zur a priori Berechnung der Stichprobengröße ist es notwendig, den zu erwartenden Effekt zu bestimmen. Laut Studienleiter sind keine vergleichbaren Studien für die Korrelation zwischen CXCR4 PET Signal und dem PET-Uptake in SSc-ILD bekannt. Daher wird auf die Zusammenhänge zwischen CXCR4-PET Signal und Lungenfunktionsparametern bei einer vergleichbaren Erkrankung (idiopathische pulmonale Fibrose) zurückgegriffen.¹ Der klinisch am besten passende Effekt zwischen Lungenfunktionsparametern (sog. FVC, forcierte Vitalkapazität) und CXCR4-PET Signal beträgt $r = -0,75$.

Der Berechnung der Fallzahl liegen somit folgende Prämissen zugrunde:

- Der Fehler 1. Art (α -Fehler) wird gemäß Konvention auf $\alpha = 0,05$ festgelegt, da keine überproportional hohen Kosten für einen Fehler 1. Art zu erwarten sind.
- Der Fehler 2. Art (β -Fehler) wird gemäß Konvention auf $\beta = 0,20$ festgelegt, da keine überproportional hohen Kosten für einen Fehler 2. Art zu erwarten sind. Die Power beträgt somit $(1 - \beta) = 0,80$.²
- Es werden *zweiseitige Hypothesentests* zugrunde gelegt.³
- Die noch relevante, relative Effektstärke ist $r = -0,75$.
- Der zu bestimmende Zusammenhang wird durch die *Pearson-Korrelationen* ermittelt. Eine Verletzung der parametrischen Voraussetzungen ist nicht zu erwarten.

Die Berechnung der Teststärke mittels der Standard-Software G*Power 3.1 ergibt eine Stichprobengröße von 11 Personen. Bei Forschungsvorhaben sollte mit einem Ausfall von Studienteilnehmern gerechnet werden. Unter Berücksichtigung dieser generellen Ausfallrate und basierend auf den Erfahrungswerten der Studienleiter sei eine Ausfallquote von 10 % als konservative Schätzung anzunehmen.

Somit ergibt sich eine Gesamtteilnehmerzahl von $N = 12$.

Adelebsen, 29. September 2021

[name] [name]

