8.1. Case number estimate

The case number estimate was carried out in collaboration with [name] and resulted in a total number of 12 participants. The complete case number estimate is attached to the study protocol.

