8.2. Biometric analyses and data evaluation

Due to the number of cases, the statistical evaluation mainly comprises exploratory analysis methods. The primary question (maximum tracer uptake in the ILD area versus normal lung tissue) is evaluated using Kendall's tau correlation coefficient.

If possible, subgroups could be examined in relation to limited vs. extensive ILD (Goh et al. 2008) with regard to stratification analogous to the INBUILD study (Flaherty et al. 2019) and with regard to the EUSTAR activity index (Valentini et al. 2017).

9. Data protection, data storage

Personalized data will be collected as part of the study. External cooperation partners, such as the statistician conducting the analysis, will only receive personal data in pseudonymized form. The data will be anonymized for the purpose of scientific publication in a peer-reviewed journal.

The data will be stored in locked rooms at the rheumatology outpatient clinic (A3, -1, ZIM) and on the UKW servers. At the end of the evaluation, but no later than after 10 years, the data collected as part of the study will be anonymized and personal data will be deleted. Any remaining sample material will be destroyed.

Until the data is anonymized, patient-related data records can be deleted and any samples that may be available can be destroyed if the patient revokes their consent.

All data is subject to the data protection regulations applicable throughout the clinic. Test subject data will not be passed on to third parties. The names of the test subjects and all other confidential information are subject to confidentiality and the provisions of the Federal Data Protection Act (BDSG). The pilot study is for research purposes only and its data will not be used (even in the future) for a consultation evaluation procedure.

All patient-related data is recorded in pseudonymized form, and an Excel-based eCRF is created for each patient. Each patient is uniquely identified by a patient number assigned during registration. [name] maintains a confidential patient list in which the pseudonyms are linked to the full patient names. The evaluation of the collected image data is stored in SAP as a findings document. The data collected for the evaluation of the pilot series is also stored as a pseudonymized Excel file, which contains only the data and the study code of the respective patient.

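### The 80% power behind N = 12 belongs to a Pearson correlation with a borrowed effect, not to the Kendall's tau analysis named for the primary question

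*Protocol*

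**What the plan says.** **Protocol, Section 16 (Appendix).** The appendix is headed as an a priori power analysis for this project.

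- The type I error "wird gemäß Konvention auf $\alpha = 0,05$ festgelegt", tests are two-sided, and power is 0.80.
- No direct evidence on the effect was available. According to the study lead there are "keine vergleichbaren Studien für die Korrelation zwischen CXCR4 PET Signal und dem PET-Uptake in SSc-ILD bekannt" (no comparable studies known).
- The effect is therefore taken from idiopathic pulmonary fibrosis: "Der klinisch am besten passende Effekt zwischen Lungenfunktionsparametern (sog. FVC, forcierte Vitalkapazität) und CXCR4-PET Signal" is given as r = -0.75.
- The statistic is Pearson's correlation, with the remark "Eine Verletzung der parametrischen Voraussetzungen ist nicht zu erwarten" (no violation of the parametric assumptions expected).
- The calculation "ergibt eine Stichprobengröße von 11 Personen". Dropout is handled by "eine Ausfallquote von 10 % als konservative Schätzung anzunehmen", which leads to N = 12.

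**Protocol, Section 8.1.** The estimate "resulted in a total number of 12 participants". The section refers to the attached estimate and does not itself mention the proxy.

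**Protocol, Section 8.2.** "The primary question (maximum tracer uptake in the ILD area versus normal lung tissue) is evaluated using Kendall's tau correlation coefficient". The section describes the analysis as mainly exploratory and states no power.

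**The concern.** A power figure belongs to one test, one pair of variables and one effect size. Here two of the three are fixed differently in two parts of the same document, and the third is missing.

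- **Test.** The appendix uses Pearson; Section 8.2 uses the rank-based Kendall's tau.
- **Variables.** The appendix's effect relates tracer signal to FVC in another disease. Section 8.2 relates uptake in diseased lung to uptake in normal lung in systemic sclerosis. The appendix describes its own target only as a correlation of PET signal with PET uptake and never names normal lung. The negative sign of r has no evident meaning for the contrast in Section 8.2.
- **Effect size.** No section gives an expected effect for ILD area against normal lung.

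The risk is one of interpretation. If Kendall's tau comes out weak or null, a reader who knows that N = 12 came from an 80% power calculation may take the result as evidence against an association. Nothing in the protocol supports that reading.

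**Working it through.** **Inputs (Section 16):** two-sided alpha 0.05; power 0.80; |r| = 0.75; Pearson; n = 11; dropout 10%; N = 12. **Input (Section 8.2):** Kendall's tau.

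**1. Reproducing the appendix's figure.**

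Fisher z approximation: n = [(z₀.₉₇₅ + z₀.₈₀) / atanh(r)]² + 3 = [(1.960 + 0.842) / 0.973]² + 3 = 11.29.

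The approximation would round up to 12. Simulating the Pearson t-test itself on bivariate normal data with |rho| = 0.75 gives power 0.78 at n = 10 and 0.83 at n = 11. So n = 11 is the smallest size with at least 80%, and the appendix's figure stands for the test it names.

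**2. Moving to the test in Section 8.2.**

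Under bivariate normality, tau = (2/π)·arcsin(rho), so |rho| = 0.75 corresponds to tau = (2/π)·arcsin(0.75) = 0.54. The Kendall test rejects when |S| (concordant minus discordant pairs) reaches the exact two-sided 5% critical value. Simulated power (400,000 samples per n):

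| n | Critical \|S\| | Actual size | Kendall power | Pearson power |
|---|---|---|---|---|
| 10 | 23 | 0.0466 | 0.65 | 0.78 |
| 11 | 27 | 0.0405 | 0.68 | 0.83 |
| 12 | 30 | 0.0447 | 0.75 | 0.87 |
| 13 | 34 | 0.0422 | 0.79 | 0.90 |
| 14 | 37 | 0.0472 | 0.84 | 0.92 |

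Even with the appendix's own effect and no dropout, Kendall's tau stays below 80% at the planned size. The gap to Pearson is about 14 points at n = 11 and 11 points at n = 12.

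**3. Effect at which Kendall's tau would reach 80%.**

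- n = 11: |rho| about 0.81 (tau 0.60), power 0.81.
- n = 12: |rho| about 0.78 (tau 0.57), power 0.81.

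**4. Range over assumed effects.** The effect for the primary question is not in the protocol, so these are assumptions:

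| tau (rho) | Kendall power, n = 11 | Kendall power, n = 12 |
|---|---|---|
| 0.33 (0.50) | 0.27 | 0.31 |
| 0.54 (0.75) | 0.68 | 0.75 |
| 0.75 (0.92) | 0.98 | 0.99 |

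The spread, from under one third to almost certainty, is why no single power can be attached to the primary analysis.

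**5. Dropout line.** 11 / 0.9 = 12.2, which rounds up to 13. Enrolling 12 with 10% loss leaves 12 × 0.9 = 10.8 evaluable on average. Averaged over a Binomial(12, 0.9) number of evaluable patients, Pearson power is still 0.81, so this slip is minor.

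**The case against.** The best defence is that the 80% is never claimed for Kendall's tau. It appears only in the appendix, next to its premises (Pearson, r = -0.75, two-sided). Section 8.2 states no power and no significance level and calls the analysis mainly exploratory. The proxy is disclosed and reasoned, and Section 8.1 points the reader to the full estimate. A rank method at n = 12 can be defended as caution. The Kendall figures also depend on the very effect said not to fit the primary contrast, and part of the shortfall is discreteness: a test at an exact 5% level would have about 71% power at n = 11 and 77% at n = 12. Section 4 plans to size the next study from the collected data, so the consequences are small.

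Much of this is fair. The arithmetic for Pearson is right, so the defect is better called an internal inconsistency than an arithmetic error. Using a proxy is not itself a fault. The dropout slip changes almost nothing, and because Section 5.1 ends participation with the PET/CT examination, later losses cannot affect the primary measurement.

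The objection does not remove the inconsistency. The appendix is presented as the power analysis for this project, and Section 8.1 takes N = 12 from it. The proxy's disclosure explains the choice of effect but not the change of test. Removing the discreteness still leaves power below 80% under the proxy. Both passages are already fixed in the protocol, so this is not a detail left to a later analysis plan.

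**Conclusion.** The concern holds: the stated 80% does not belong to the planned primary analysis. The true power of that analysis is unknown and cannot be computed from the protocol; it is unsupported rather than demonstrably low.

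The figures of about 68% (n = 11) and 75% (n = 12) are an illustration. They assume that the proxy effect applies to the primary question, bivariate normality, no ties and the exact two-sided test. They show only that the change of test alone matters, by 11 to 14 points, even if everything else in the appendix is granted.

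This should be corrected, but it does not threaten the study. The pilot is exploratory, and 12 patients can be justified without a power claim.

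**What to change.** Keep 12 patients and change the wording.

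1. **Section 8.1 and the appendix.** Suggested text: N = 12 rests on a proxy effect (r = -0.75, uptake against FVC in idiopathic pulmonary fibrosis). The 80% power applies only to a two-sided Pearson correlation of that size (83% at n = 11). No effect size is available for ILD area against normal lung, so no power is claimed for the primary analysis. If the proxy effect applied, and under bivariate normality, Kendall's tau would have about 68% power at n = 11 and 75% at n = 12.
2. **Section 8.2 and the appendix.** Name the same test in both. If Kendall's tau stays, remove or explain the appendix's remark on parametric assumptions.
3. **Dropout line.** State that 12 enrolled with 10% loss leaves about 10.8 evaluable, and that keeping 11 would need 13.

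The last sentence of item 1 is the least essential. A detectable effect for a paired comparison belongs here only if Section 8.2 is itself changed to a paired comparison.

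The cost is a few sentences in Sections 8.1, 8.2 and 16, with no extra patients and no change of procedure. The protocol gives up any claim of 80% power for its primary analysis.
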